6.4. Analyses of Secondary Efficacy Endpoint

For the binary endpoints defined as ≥ 4 -point reduction (improvement) from the baseline visit in either the whole body itch NRS score or the scalp itch NRS score at post-baseline visits, the analyses will be based on subjects in the ITT population with baseline whole body itch NRS score ≥ 4 or baseline scalp itch NRS score ≥ 4 , respectively. For the continuous secondary endpoint (i.e. change from baseline in DLQI total score at Week 16), the analyses will be based on ITT population. Unadjusted 2-sided p-values and 2-sided 95% confidence intervals (CIs) (ie, without multiplicity adjustment) will be reported.

6.4.1. Whole Body Itch Numeric Rating Scale (NRS) and Scalp Itch Numeric Rating Scale (NRS) Assessments

In order to evaluate the onset of effect of apremilast 30 mg BID compared to placebo for itch, the following secondary endpoints are specified.

- Whole Body Itch NRS Response: Proportion of subjects with ≥ 4 -point reduction (improvement) from baseline in the whole body itch NRS score at Week 16
- Scalp Itch NRS Response: Proportion of subjects with ≥ 4 -point reduction (improvement) from baseline in the scalp itch NRS score at Week 16
- Whole Body Itch NRS Response: Proportion of subjects with ≥ 4 -point reduction (improvement) from baseline in the whole body itch NRS score at Week 12, Week 8, Week 4, and Week 2
- Scalp Itch NRS Response: Proportion of subjects with ≥ 4 -point reduction (improvement) from baseline in the scalp itch NRS score at Week 12, Week 8, Week 4, and Week 2

Statistical analyses for the 10 endpoints will be performed 1 by 1 downward from Week 16 to Week 2. Multiplicity adjustment is specified in Section 6.2.

These binary endpoints will be analyzed similarly as the primary endpoint. The treatment difference between apremilast 30 mg BID and placebo will be compared using CMH test adjusting for the stratification factor at randomization. The 2-sided p-values from the CMH test, the adjusted treatment difference in proportion using the weighted average of the treatment differences across the strata with the CMH weights, along with the associated 2-sided 95% CIs using a normal approximation to the weighted average will be provided.

The SAS procedure MI will be used to impute missing whole body itch NRS score (or scalp itch NRS score) at the scheduled analysis visits in the Placebo-controlled Phase (Weeks 0 to 16) to create M=25 complete data sets. The missing data patterns will be checked by treatment and stratification factor at Baseline (Week 0), and Weeks 2, 4, 8, 12 and 16. If there are non-monotone missing patterns, two separate imputation procedures will be used to complete the imputation process.

In the first step, the Markov Chain Monte Carlo (MCMC) method will be used to impute missing scores by treatment and stratification factor to create M=25 imputed data sets with monotone missing patterns. The minimum and the maximum values for imputation will be 0 and 10, which correspond to the lowest and the highest whole body itch NRS score (or scalp itch NRS score). The seed will be set to 804529, the imputed values will be rounded to integers and a single chain will be used to produce imputations. In case there are convergence issues, a simple model will be used to impute the missing scores by treatment, with further simplification by dropping both treatment and stratification factor in imputation model if necessary.

In the second step, the predictive mean matching method will be used to impute the remaining missing values for the 25 data sets with monotone missing patterns. The MONOTONE REGPMM statement will be used with seed 447159. The missing values at each visit will be imputed based on treatment, stratification factor, and whole body itch NRS score (or scalp itch

NRS score) at baseline and previous visits. The number of closest observations to be used in the selection will be K=5.

After the completion of imputation, the same CMH method will be used to analyze the 25 complete data sets and the SAS procedure MIANALYZE will be used to combine the results for the statistical inferences.

In summary, the primary analysis of whole body Itch NRS response (or scalp Itch NRS response) will be performed separately for each post baseline visit in the Placebo-controlled Phase for ITT population using MI method for treating missing values. Supportive analyses will be performed at Week 16 visit for: (1) ITT population treating missing values using the LOCF method, (2) ITT population treating missing values using NRI method. In addition, analyses using CMH test adjusting for the stratification factor at randomization and pooled site will be performed at Week 16 for ITT population using MI method for imputing missing values.

6.4.2. Change from Baseline in Dermatology Life Quality Index (DLQI) Total Score at Week 16

Change from baseline in DLQI total score at Week 16 will be analyzed based on the ITT population using the analysis of covariance (ANCOVA) model. The ANCOVA model will use the change from baseline as the dependent variable and will include treatment group and stratification factor as independent variables and the baseline value as a covariate variable. Within-group least-squares (LS) mean changes from baseline at Week 16, the associated standard errors (SEs) and 2-sided 95% CIs, treatment differences in LS mean changes from baseline, and the associated 2-sided 95% CIs and p-values, will be derived from the ANCOVA model.

The SAS procedure MI will be used to impute missing DLQI total score at the scheduled analysis visits in the Placebo-controlled Phase (Weeks 0 to16) to create M=25 complete data sets. The missing data patterns will be checked by treatment and stratification factor at Baseline (Week 0), and Weeks 4, 8 and 16. If there are non-monotone missing patterns, two separate imputation procedures will be used to complete the imputation process.

In the first step, the Markov Chain Monte Carlo (MCMC) method will be used to impute missing scores by treatment and stratification factor to create M=25 imputed data sets with monotone missing patterns. The minimum and the maximum values for imputation will be 0 and 30, which correspond to the lowest and the highest DLQI total score. The seed will be set to 804529, the imputed values will be rounded to integers and a single chain will be used to produce imputations. In case there are convergence issues, a simple model will be used to impute the missing scores by treatment, with further simplification by dropping both treatment and stratification factor in imputation model if necessary.

In the second step, the predictive mean matching method will be used to impute the remaining missing values for the 25 data sets with monotone missing patterns. The MONOTONE REGPMM statement will be used with seed 447159. The missing values at each visit will be imputed based on treatment, stratification factor, and DLQI total score at baseline and previous visits. The number of closest observations to be used in the selection will be K=5.

After the completion of imputation, the same ANCOVA model will be used to analyze the 25 complete data sets and the SAS procedure MIANALYZE will be used to combine the results for the statistical inferences.

In summary, the secondary analysis of change from baseline in DLQI total score at Week 16 will be performed for ITT population using MI method for treating missing values. Sensitivity analysis will be performed for ITT population treating missing values using the LOCF method,

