The continuous endpoint (ie, change from baseline in DLQI total score at Week 16) will be analyzed based on the ITT population using the analysis of covariance (ANCOVA) model. The ANCOVA model will use the change from baseline as the dependent variable and will include treatment group and stratification factor as independent variables and the baseline value as a covariate variable. Within-group least-squares (LS) mean changes from baseline at Week 16, the associated standard errors (SEs) and 2-sided 95% CIs, treatment differences in LS mean changes from baseline, and the associated 2-sided 95% CIs and p-values, will be derived from the ANCOVA model. Missing values at Week 16 will be imputed using the MI method, with sensitivity analysis using the LOCF method.

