5.4. Time Points

Time points in all analyses are based on the remapped visits/study weeks using the following visit mapping algorithm, which may or may not be the same as the visits/study weeks as recorded in the database.

Post baseline time points in all analyses will be captured based on analysis visit window (range of study days) around the target day for each analysis visit, based on the actual day of evaluation relative to a reference date. Appropriate dates will be used to calculate the study day, e.g., date of measurement or date of specimen collection will first be used, and then the date of visits/study weeks as recorded in the database will be used. If there are multiple measurements within a time point based on the study day, then the non-missing value from the closest measurement to the planned study day will be used for that visit. If the value at a scheduled visit is missing and there is no value available within the time window based on the study day, the value at the study week will be missing.

Table 2: Table for Visit Mapping for by Time Point Analysis

Analysis Visit	Target Day	Visit Window
Baseline	1	≤ 1
Placebo-controlled Phase		
Week 2	15	2 – 21
Week 4	29	22 – 42
Week 8	57	43 – 70
Week 12	85	71 – 98
Week 16	113	99 – End of Phase
Apremilast Extension Phase		
Week 20	141	Start of Phase – 154
Week 24	169	155 – 196
Week 32	225	197 – End of Phase

Note: Target day and visit window are relative to the date of Visit 2/Week 0 (Day 1) for randomization. Definitions for baseline and start or end of the phases are specified in Section 5.1 and 5.3 for both efficacy and safety analysis.

Time points in the analyses or summaries of efficacy data over time include the scheduled study weeks per protocol, the end of a study phase, and the observational follow-up visit. Appropriate dates (e.g., date of measurement or date of specimen collection) will first be used to ensure only data (including data from scheduled, unscheduled, discontinuation, and observational follow-up visits) measured or collected within the specific analysis phase (as defined in Section 5.1) being analyzed or summarized are included, and then the visits/study weeks as recorded in the database will be used to assign one value (possibly missing) to each time point at the subject level. It is possible that multiple assessment values will fall into the same visit window. The following rule may be used to select the unique value for that analysis visit:

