6.5.3. Dermatology Life Quality Index (DLQI)

The endpoints include:

- Change from baseline in DLQI total score at Weeks 4, 8, 16 and 32
- Change from baseline in DLQI subscale scores at Weeks 4, 8, 16 and 32

CCI
C
I

Mean change from baseline in DLQI total score and subscale scores will be summarized by treatment group and time point using descriptive statistics. Analysis for the Week 16 change from baseline in DLQI total score is presented in the secondary efficacy endpoint Section 6.4.2.

CCI

Week 16 DLQI

response will be analyzed similarly as the primary and secondary binary endpoint. The treatment difference between apremilast 30 mg BID and placebo will be compared using CMH test adjusting for the stratification factor at randomization. The 2-sided p-values from the CMH test, the adjusted treatment difference in proportion using the weighted average of the treatment differences across the strata with the CMH weights, along with the associated 2-sided 95% CIs using a normal approximation to the weighted average will be provided. The analysis will be based on ITT population with missing values imputed using the LOCF method.

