6.5.4. Whole Body Itch and Scalp Itch Numeric Rating Scale (NRS) Assessment

The endpoints include:

- Whole body itch NRS score by visit
- Scalp itch NRS score by visit
- Change from baseline in whole body itch NRS score by visit
- Change from baseline in scalp itch NRS score by visit

All endpoints will be summarized by treatment group and time point using descriptive statistics.

Shift tables for shifts from baseline to post-baseline visits and End of Phase (LOCF) will be provided by treatment and time point for whole body itch NRS score and scalp itch NRS score.

CCI

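### Does the SAP need to say which DLQI scores the Week 16 LOCF analysis may carry forward?

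*SAP*

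**What the plan says.** Protocol Table 3 schedules DLQI at baseline and at Weeks 4, 8 and 16 of the controlled phase. It is also completed at early termination (Table 3, footnote b; Protocol 6.2.1). It is not collected at the follow-up visit.

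On missing data, Protocol 9.6.1.2 says: "Missing values at Week 16 will be imputed using the MI method, with sensitivity analysis using the LOCF method". SAP 6.4.2 fixes the imputation visits ("The missing data patterns will be checked by treatment and stratification factor at Baseline (Week 0), and Weeks 4, 8 and 16") and closes with "Sensitivity analysis will be performed for ITT population treating missing values using the LOCF method". For the exploratory Week 16 DLQI response, SAP 6.5.3 says: "The analysis will be based on ITT population with missing values imputed using the LOCF method". The readable text contains no definition of LOCF; some SAP sections are blacked out.

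SAP 5.4 sets the general rules. "Time points in all analyses are based on the remapped visits/study weeks using the following visit mapping algorithm", and Table 2 gives one set of windows for every endpoint. Eligible efficacy data include "data from scheduled, unscheduled, discontinuation, and observational follow-up visits", provided they were measured within the phase being analysed. The efficacy time points are "the scheduled study weeks per protocol, the end of a study phase, and the observational follow-up visit". Where several scores fall in one window, the one closest to the target day is kept. SAP 6.5.4 then joins the end of a phase to LOCF for the itch shift tables ("End of Phase (LOCF) will be provided by treatment and time point for whole body itch NRS score and scalp itch NRS score"), and SAP 6.5.6 does the same for ScPGA.

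**The concern.** A subject who stops early can have a DLQI score whose Table 2 label is a week at which DLQI is not scheduled. The imputation list skips such scores, and SAP 6.4.2 does not say whether LOCF skips them too. Three readings can be written down:

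- **A:** carry the last post-baseline score in the phase, including the discontinuation visit.
- **B:** carry the Week 4 or Week 8 analysis value, or baseline if there is neither.
- **C:** as B, but a subject with neither value has no result.

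LOCF is the only sensitivity analysis for this ranked endpoint and the only missing-data method for the DLQI response. If it disagreed with multiple imputation, a reader might not know whether the method or the set of scores was the cause.

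**Working it through.** **1. Is the imputation list a gap?** No. SAP 6.4.2 names the visits, and they are the scheduled ones. Adding Weeks 2 and 12 would not help. Apart from unscheduled assessments, a DLQI labelled Week 2 or Week 12 exists only for subjects who stopped, so the data hold almost no pairs from which to regress Week 16 on it.

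**2. Which days are affected for DLQI?** Inputs: the Table 2 windows and the closest-to-target rule. Assume that scheduled visits fall on target (Days 29 and 57).

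| Discontinuation visit on day | Table 2 label | Days | Do A and B use the same score? |
|---|---|---|---|
| 2-21 | Week 2 | 20 | No |
| 22-29 | Week 4 | 8 | Yes |
| 30-42 | Week 4 | 13 | No: the Day 29 score is closer to target |
| 43-57 | Week 8 | 15 | Yes |
| 58-70 | Week 8 | 13 | No: the Day 57 score is closer to target |
| 71-98 | Week 12 | 28 | No |

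Unscheduled labels cover 20 + 28 = 48 of 97 days (49%). The closest-to-target rule adds 13 + 13 = 26, giving 74 of 97 (76%). From Day 99 the score is the Week 16 value itself.

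**3. Is this special to DLQI?** No. ScPGA and itch are scheduled on target Days 15, 29, 57 and 85, so the closest-to-target rule can set aside a discontinuation score on Days 16-21, 30-42, 58-70 and 86-98: 6 + 13 + 13 + 13 = 45 of 97 days. The question is one of ordinary LOCF programming for all three measures.

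**4. How many subjects?** Assume 10-20% of 300 stop (30 to 60), evenly over Days 2-98, and 50-100% attend the early termination visit.

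- Unscheduled labels only: 30 × 0.5 × 48/97 = 7, up to 60 × 1.0 × 48/97 = 30.
- All 74 days: 30 × 0.5 × 74/97 = 11, up to 60 × 1.0 × 74/97 = 46.
- No post-baseline score at all (stopped on Days 2-28 without attending): none at full attendance; at 50%, 30 × 0.5 × 27/97 = 4, up to 60 × 0.5 × 27/97 = 8.

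**5. How much does the estimate move?** A simulation covered the unscheduled labels. Its assumed inputs were 200 against 100 subjects, baseline mean 13 (SD 7), Week 16 change -6 against -3 (SD 4), visit noise SD 3, 10% or 20% dropout in several patterns, and the planned ANCOVA, over 18 scenarios of 2000 trials.

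- Mean difference: A-B -0.09 to 0.00; A-C -0.09 to +0.14; B-C -0.02 to +0.16.
- Highest minus lowest reading within one trial: 0.11-0.21 on average, 95th percentile 0.22-0.40. The standard error is about 0.55.
- One scenario (fast onset, random 20% dropout): complete data -2.51, A -2.46, B -2.41, C -2.51.

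The simulation does not count the 26 extra days. If each moved the estimate as much as a simulated day, the largest mean A-B gap would be 0.09 × 74/48 = 0.14 points, or 0.14/0.55 = 0.25 standard errors. That is generous, because on those days the two scores are at most 13 days apart.

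**The case for a change.** The best case for writing the rule down is this. SAP 5.4 decides which data are mapped to time points, not what LOCF carries, and the same section did not bring Weeks 2 and 12 into the DLQI imputation. The end-of-phase label is attached to itch and ScPGA shift tables, not to DLQI. The sponsor spells out an end-of-phase value, as the last post-baseline one, only for vital signs and weight (SAP 11.4). The case of no post-baseline score is settled nowhere in the readable text. Within a single trial the readings can also lie up to 0.71 standard errors apart at the 95th percentile.

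It is true that no sentence applies the rule to DLQI, and that the no-score case is open. It does not follow that the plan misleads. Carrying the last observation, from data that include discontinuation visits, points to A. Reading C drops subjects from an analysis said to cover the ITT population. Stating A would also leave LOCF and imputation using different score sets, so it would not resolve the worry about explaining a disagreement between them.

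**Conclusion.** This is a gap that analysts fill sensibly, and no change to the plan follows. No stated rule gives a wrong result. The imputation visits are given, and the general rules in SAP 5.4 make the last score in the phase the default for LOCF. The few subjects with no post-baseline score are a routine programming decision.

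The size is small: mean differences of 0.00-0.16 points between readings in simulation, or 0.14 between A and B after the generous scaling, against a standard error of about 0.55. DLQI is last of 12 ranked tests, and its test rests on multiple imputation, which LOCF does not touch. The ScPGA and itch endpoints likewise rest on imputation, with NRI as a further check at Week 16.

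These sizes depend on assumed dropout, attendance and DLQI values, because the documents give none. The day counts also assume scheduled visits on target, whereas the protocol allows 4 days either side.

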6.5. Analyses of Exploratory Efficacy Endpoints

Descriptive summary statistics or proportion of subjects achieving specified criteria will be summarized by treatment group. When appropriate, exploratory endpoints at Week 16 will also be analyzed using CMH or ANCOVA methods similar to the primary and secondary endpoints based on ITT population with missing values imputed using LOCF method.

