###### **9.6.1.1. Primary Efficacy Endpoint**

The primary endpoint is the proportions of subjects who achieving ScPGA response at Week 16 (defined as ScPGA score of clear [0] or almost clear [1] with at least a 2-point reduction from baseline at Week 16). It will be analyzed using the ITT population. A sensitivity analysis will be performed using the PP population.

The treatment difference between apremilast 30 mg BID and placebo will be compared using CMH (Cochran–Mantel–Haenszel) test adjusting for the stratification factor at randomization. The 2-sided p-values from the CMH test, the adjusted treatment difference in proportion using the weighted average of the treatment differences across the strata with the CMH weights, along with the associated 2-sided 95% CIs using a normal approximation to the weighted average will be provided. Missing values at Week 16 will be imputed using the multiple imputation (MI) method (SAS Institute Inc. 2008) as the primary analysis, with sensitivity analysis using the last observation carried forward (LOCF) method and the non-responder imputation (NRI) method.

The SAS procedure MI will be used to impute missing ScPGA scores at the scheduled assessments in the Placebo-controlled Phase (Weeks 0-16) to create M=25 complete data sets. The missing data patterns will be checked by treatment and stratification factor at Baseline (Week 0), and Weeks 2, 4, 8, 12 and 16. If there are non-monotone missing patterns, two separate imputation procedures will be used to complete the imputation process.

In the first step, the Markov Chain Monte Carlo (MCMC) method will be used to impute missing scores by treatment and stratification factor to create M=25 imputed data sets with monotone missing patterns. The minimum and the maximum values for imputation will be 0 and 4, which correspond to the lowest and the highest ScPGA scores. The seed will be set to 804529, the imputed values will be rounded to integers and a single chain will be used to produce imputations.

In the second step, the predictive mean matching method will be used to impute the remaining missing values for the 25 data sets with monotone missing patterns. The MONOTONE REGPMM statement will be used with seed 447159. The missing values at each visit will be imputed based on treatment, stratification factor, and ScPGA scores at baseline and previous visits. The number of closest observations to be used in the selection will be K=2.

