#### **9.6.1.4. Exploratory Endpoints**

Descriptive summary statistics or proportion of subjects achieving specified criteria will be summarized by treatment group. When appropriate, exploratory endpoints at Week 16 will also be analyzed using CMH or ANCOVA methods similar to the primary and secondary endpoints.

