6. STATISTICAL METHODOLOGY FOR EFFICACY

6.1. General Approaches to Efficacy Analysis

All efficacy evaluations will be conducted using the ITT population. Supportive analysis of the primary efficacy endpoint using the PP population will be conducted.

The summary and analyses of the primary and secondary endpoints evaluated at or prior to Week 16 will be performed by treatment (placebo vs. apremilast 30 mg BID). Statistical comparisons will be made between apremilast 30 mg BID and placebo; the null hypothesis is that the effects of the two treatments (i.e., placebo vs. apremilast 30 mg BID) have no difference.

Descriptive statistics (n, mean, SD, median, Q1, Q3, min, max) will be presented for appropriate endpoints at specified time points. Specifically, for continuous variables, descriptive statistics for baseline and change (or percentage change) from baseline will be provided. Categorical variables will be summarized with frequency tabulations; shift tables will be provided when appropriate.

For discrete variables, the response rate and its 95% confidence interval (CI) will be calculated by treatment. Treatment difference will be tested using the Cochran-Mantel-Haenszel (CMH) test adjusting for the stratification factor at randomization (baseline ScPGA score moderate (3) or severe (4)) for the Double-blind Placebo-controlled Phase. The difference of response rate (apremilast 30 mg BID - placebo) and its 95% CI as well as the p-value will be produced using CMH method.

The continuous endpoints will be analyzed using the analysis of covariance (ANCOVA) model with treatment group and stratification factor as independent variables and the baseline value as a covariate variable. SAS Proc Mixed will be used for the analysis. The least square means (LS mean) with 95% CI for each treatment and difference of LS mean (apremilast 30 mg BID - placebo) with 95% CI as well as the p-value will be provided.

For the primary and the secondary efficacy endpoints, the primary approach in handling missing data will be the multiple imputation (MI) methods. Statistical outputs from the imputed complete data sets will be combined in making statistical inferences.

Efficacy results will be considered statistically significant after consideration of the strategy for controlling the Type I error rate that is described in Section 6.2. All statistical tests will be two-sided and be conducted at the 0.05 significance level, and p-values will be reported.

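### Week 16 DLQI response is analysed with LOCF alone, while Week 16 change in DLQI total score uses multiple imputation

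*SAP*

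**What the plan says.** SAP 6.5 provides for CMH or ANCOVA comparisons of exploratory endpoints at Week 16, "similar to the primary and secondary endpoints based on ITT population with missing values imputed using LOCF method".

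SAP 6.5.3 says Week 16 DLQI response is to be handled like the primary and secondary binary endpoints, with a CMH p-value, a CMH-weighted difference and a 95% CI. It then closes: "The analysis will be based on ITT population with missing values imputed using the LOCF method". SAP 6.5.6 ends with the same sentence, attached to an endpoint that is redacted. The readable text of these sections plans no MI or non-responder analysis of these comparisons.

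Elsewhere the roles are reversed. SAP 6.1: "For the primary and the secondary efficacy endpoints, the primary approach in handling missing data will be the multiple imputation (MI) methods". SAP 6.3, 6.4.1 and 6.4.2 specify that MI, with 25 data sets, and give LOCF a supportive or sensitivity role. Protocol 9.6.1.1 likewise makes MI the primary analysis, "with sensitivity analysis using the last observation carried forward (LOCF) method and the non-responder imputation (NRI) method".

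For the DLQI total score, SAP 6.5.3 points to the MI analysis: "Analysis for the Week 16 change from baseline in DLQI total score is presented in the secondary efficacy endpoint Section 6.4.2".

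Protocol 9.6.1.4 says only: "When appropriate, exploratory endpoints at Week 16 will also be analyzed using CMH or ANCOVA methods similar to the primary and secondary endpoints".

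**The concern.** DLQI total-score change and DLQI response come from the same questionnaire, visit and ITT subjects. One is imputed by MI, the other by carrying a value forward. If they disagree, the reader cannot tell a real difference between mean change and response rate from the effect of the rule.

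LOCF also has a known weakness here. DLQI is scheduled only at baseline and Weeks 4, 8 and 16 in the placebo-controlled phase, so a carried value may come from half-way through the phase or earlier. If scores are still improving, dropouts are held at an early, lower response. If dropout differs between arms, so does the error. The carried value is then analysed as if it had been observed.

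Unequal dropout is plausible from the documents: the first week is titrated to reduce gastrointestinal side effects (Protocol 7.1), and lack of efficacy is a listed reason for stopping treatment (Protocol 11.1).

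**Working it through.** **Design figure.** The plan states no size for LOCF or MI bias. Its related figure is the sample size (Protocol 9.3, SAP 4.4): about 300 subjects, 2:1, 38% vs 20%, two-sided 0.05, 90% power. With allocation ratio k = 2 and average rate (0.20 + 2 × 0.38)/3 = 0.32:

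n(placebo) = [1.960 × √(1.5 × 0.32 × 0.68) + 1.282 × √(0.20 × 0.80 + 0.38 × 0.62/2)]² / 0.18² = (1.120 + 0.675)² / 0.0324 ≈ 99.5, so 100.

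That gives 100 + 200 = 300, with power 0.902. The figure reproduces. It sets the arm sizes below; the point does not depend on it.

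**Simulation inputs from the documents.** 200 apremilast and 100 placebo; a 0 to 30 score at baseline and Weeks 4, 8 and 16; MI by predictive mean matching with K = 5 on treatment, stratum and earlier scores (SAP 6.4.2); CMH-weighted difference in proportions.

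**Assumed inputs.** Dropout rates, means and SDs, since the documents give none. Response is taken as a reduction of at least 5 points in total score, because the definition is redacted. Mean improvement at Weeks 4 and 8 is 55% and 80% of the Week 16 value. Dropout is monotone and missing at random, depending on the last observed change. LOCF may carry baseline. There were 5 imputations instead of 25, and 250 replicates per scenario.

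Shift = mean estimate under the method minus mean full-data estimate, in percentage points:

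| Dropout, apremilast / placebo | Full-data difference | LOCF shift | MI shift |
|---|---|---|---|
| 5% / 5% | 23.0 | −0.76 | 0.00 |
| 10% / 10% | 23.2 | −1.71 | −0.32 |
| 15% / 15% | 22.2 | −2.17 | −0.10 |
| 20% / 20% | 23.0 | −3.15 | −0.34 |
| 15% / 10% | 22.6 | −3.34 | −0.16 |
| 25% / 15% | 22.2 | −6.57 | −0.02 |
| 10% / 20% | 21.8 | +0.80 | −0.20 |
| 20% / 10%, no effect | 0.4 | −2.27 | +0.11 |
| 15% / 15%, no effect | −0.6 | +0.29 | +0.16 |
| 10% / 20%, no effect | −0.4 | +2.28 | −0.12 |

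The Monte Carlo standard error of the MI shift was 0.07 to 0.16 points.

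**Why the sign changes.** Let d be the dropout fraction in an arm and g the LOCF response rate minus the true response rate among its dropouts. Then LOCF shift = d(A) × g(A) − d(P) × g(P).

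- The two no-effect rows with unequal dropout give g ≈ −2.27/0.10 and −2.28/0.10, about −22.75 points. Take this as g(P).
- The four equal-dropout rows with an effect give g(A) − g(P) = −15.2, −17.1, −14.5 and −15.8, average about −15.6. So g(A) ≈ −38.4.
- Predicted for 25%/15%: 0.25 × (−38.4) + 0.15 × 22.75 ≈ −6.2 (simulated −6.57).
- Predicted for 15%/10%: −5.76 + 2.28 ≈ −3.5 (simulated −3.34).
- Predicted for 10%/20%: −3.84 + 4.55 ≈ +0.7 (simulated +0.80).

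The identity accounts for the pattern: the shift depends on dropout by arm and need not be conservative.

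**The two DLQI results side by side.** At 25%/15%, LOCF lowers the response difference from 22.2 to about 22.2 − 6.6 = 15.6 points. MI moves the ANCOVA difference in DLQI change (−2.69) by only 0.01.

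**If MI loses treatment.** The same MI with treatment and stratum removed was pulled towards no difference by 0.8 to 3.3 points in the scenarios with an effect, about as much as LOCF at equal dropout.

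**The case against.** A statistician defending the plan could say that methods are deliberately tiered by endpoint rank. The MI sentence in SAP 6.1 is limited to primary and secondary endpoints, so LOCF in SAP 6.5 does not contradict it. Exploratory endpoints are outside the testing hierarchy (SAP 6.2). An LOCF analysis of DLQI change is planned as a sensitivity analysis in SAP 6.4.2, so response and change can be compared under one rule. A discontinuation visit also collects DLQI (Protocol 6.2.1), so carried values may be more recent than the simulation allows.

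All of that stands and limits the consequence. It does not explain why a method judged only supportive for the key endpoints is the sole method here, and the SAP gives no reason.

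Four stronger readings are tempting, and the documents do not support them.

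- A reader might infer that the SAP departs from the protocol. Protocol 9.6.1.4 refers to CMH or ANCOVA methods and is silent on imputation; the SAP fills a gap.
- A reader might infer that every exploratory Week 16 result rests on LOCF. Week 16 ScPGA response and DLQI total change also appear in the exploratory lists, but are referred to the MI analyses in SAP 6.3 and 6.4.2. The exploratory itch scores are descriptive.
- A reader might size the problem on ScPGA response. That endpoint already has MI. It is also scored at Week 2 and Week 12, when DLQI is not scheduled.
- A reader might infer that LOCF always biases the difference, or always downwards. With no effect and equal dropout the shift was close to zero; with more placebo dropout it was upwards.

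**Conclusion.** The point holds as an inconsistency within the SAP. LOCF is the only readable missing-data rule for Week 16 exploratory comparisons that report p-values and CIs. DLQI response is the one clear readable case, on the assumption that its redacted definition uses the total score.

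Under the assumed dropout, LOCF moved the response difference by −6.6 to +0.8 points when the true difference was 22 to 23, and by about ±2.3 points with no effect and unequal dropout. MI stayed within about 0.3. These figures illustrate the mechanism and do not predict this trial. MI's advantage rests on data missing at random and on treatment staying in the imputation model. The convergence fallback in SAP 6.4.2 allows treatment to be dropped, though it is stated for the MCMC step; removing it from the matching regression, as above, is an upper illustration.

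No confirmatory claim is affected. This is a cheap improvement, not a flaw in the main analysis.

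**What to change.** In SAP 6.5.3, derive Week 16 DLQI response in each of the 25 data sets imputed under SAP 6.4.2, analyse each by CMH, and combine with MIANALYZE. Make this the main analysis and LOCF supportive.

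In SAP 6.5 and 6.5.6, do the same for the other Week 16 exploratory comparisons now assigned LOCF, imputing each endpoint's own score within its own range. State that treatment stays in the imputation model. If LOCF is kept as the main method, give the reason.

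The cost is a few lines of SAP text and some extra runs of existing programs; DLQI response needs no new imputation. SAP Section 2 says the plan is finalised before the Week 16 database is unblinded, so the change should be made before then.
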